6.3 Lifestyle Restrictions

There are no specific dietary restrictions in the study. It is expected that participants are aware of the importance of maintaining reasonable consistency in timing and size of meals (and specifically carbohydrate intake) for achieving adequate control of hyperglycemia but appreciate that the presence of GP may make this difficult.

For timing of meals around the GEBT, refer to the Study Reference Manual.

6.4 Screen Failures

For de novo participants, screen failures are defined as participants who consent to participate in the clinical study but are not subsequently randomly assigned to study treatment. Screen failures can fail to meet criteria for random assignment to study treatment in the study either before or after participation in the Run-in Period.

De novo participants who do not meet the criteria for participation in this study (screen failure) before entering the Run-in Period may be rescreened once if the reason for screen failure is only because of Inclusion Criterion 3 "HbA1c \leq 11.0% at Screening (Visit -2)." In this specific situation, the participant may be rescreened after at least one month and no more than 6 months of further effort to achieve improved glycemic control, as indicated by HbA1c being \leq 11.0%.

The sponsor may permit a participant with a positive urine drug screen by immunoassay, at Screening (Visit -2) to continue in the Screening Period while confirmatory urine drug screen

testing by a more specific method is carried out on an aliquot of the original urine sample. If the confirmatory test is negative, the initial positive urine drug screen will be considered to have been a false-positive urine drug screen and the participant can continue in screening.

Confirmatory testing will be done at the discretion of the sponsor and must be approved by the sponsor prior to analysis. The significance of a positive urine drug screen result for drugs prescribed for the participant (ie, barbiturates, benzodiazepines, amphetamines, but not opioid or cannabinoids) should be assessed by the Investigator as to whether their stable-dose usage is clinically appropriate, and if so, should not be exclusionary; use of the prescribed drugs on an as-needed basis is not allowed.

Rescreening of a participant for any other reason is up to the discretion of the Sponsor and must be approved by the Sponsor prior to any rescreening procedures. The timeframe for rescreening is up to 6 months from the time of screen failure. Participants who enter the Run-in Period will not be allowed to be rescreened. Rescreening requires that a participant be assigned a new participant number and after repeating the Informed Consent Process, undergo all original screening assessments.

A minimal set of screen failure information is required to ensure transparent reporting of screen failure participants to meet the Consolidated Standards of Reporting Trials (CONSORT) publishing requirements and to respond to queries from regulatory authorities. Minimal information includes demography, screen failure details, eligibility criteria, and any SAE.

7 Treatments

Study treatment is defined as any investigational treatments, marketed product, or medical device intended to be administered to a study participant according to the study protocol.

7.1 Treatments Administered

Participants who meet study entry criteria will be randomized in a 2:1 ratio to blinded treatment with relamorelin 10 µg or placebo. At Visit 1, participants will self-administer study treatment in the presence of study center personnel.

After Visit 1, participants are to self-administer study treatment twice daily SC, with the first daily dose being administered within approximately 30 minutes before the morning meal (ie, breakfast, at approximately 08:00) and the second daily dose within approximately 30 minutes before the evening meal (ie, dinner, at approximately 18:00). If a participant does not eat morning or evening meals, study treatment should be administered during typical meal times (eg, 06:00 to 09:00 and 17:00 to 20:00).

Should a participant miss a dose prior to either the morning or evening meal, he/she should adjust his/her study treatment administration as follows:

- If within 6 hours of the normal dosing time relative to the morning or evening dose, the participant should self-administer the dose at that time
- If later than 6 hours after the normal dosing time relative to the morning or evening dose, the participant should not self-administer the dose. Resume normal dosing at the next scheduled time (ie, that evening if the morning dose was missed, or the next morning if the evening dose was missed)

Participants should rotate injection sites in the abdomen.

Study treatment will be dispensed as pen injectors with pre-filled cartridges of either relamorelin or placebo. Study treatment details are provided in [Table 7-1](#).

Table 7-1 Study Treatment Details

Study Treatment	Relamorelin	Placebo
Dosage Formulation	Pre-Filled Cartridge in Multi-dose Pen Injector	Pre-Filled Cartridge in Multi-dose Pen Injector
Unit Dose Strength	10 µg dose	N/A
Route of Administration	Subcutaneous	Subcutaneous
Dosing Instructions	Administer twice daily	Administer twice daily
Packaging and Labeling	Study treatment will be provided in a single unit carton. Each carton will be labeled as required per country requirement.	Study treatment will be provided in a single unit carton. Each carton will be labeled as required per country requirement.
Manufacturer	Baxter (Prefilled Cartridge) Allergan (Assembled Pen)	Baxter (Prefilled Cartridge) Allergan (Assembled Pen)
Injection Device	Utilize Multi-dose Pen Injector for the administration of the study treatment or placebo. Refer to the Relamorelin Pen Investigational Directions for Use for detailed instructions on use of the injection device. Each pen injector is to be used for 28 days.	Utilize Multi-dose Pen Injector for the administration of the study treatment or placebo. Refer to the Relamorelin Pen Investigational Directions for Use for detailed instructions on use of the injection device. Each pen injector is to be used for 28 days.

7.1.1 Study Supplies

1. The Allergan-manufactured medical devices (or devices manufactured for Allergan by a third party) provided for use in this study are: (1) Prefilled Cartridge, and (2) Multi-dose Pen Injector.
2. Instructions for medical device use are provided in Relamorelin Pen Investigational Directions for Use.
3. Medical device incidents, including those resulting from malfunctions of the device, must be detected, documented, and reported by the investigator throughout the study (see [Appendix 7](#)).

7.2 Dose Modification

Not applicable

7.3 Method of Treatment Assignment

All participants will be centrally assigned to randomized study treatment using an interactive web response system (IWRS). Before the study is initiated, the log-in information and directions for the IWRS will be provided to each site.

At the beginning of the 52-week Treatment Period, participants will be randomized in a 2:1 ratio to blinded treatment with relamorelin 10 µg or placebo.

Study treatment will be dispensed at the study visits indicated in the SoA (Section 2).

Returned study treatment should not be re-dispensed to the participants.

7.4 Blinding/Masking

The investigator, investigational staff, and participant will be fully blinded to study treatment during the 52-week Treatment Period. All study treatment will be provided in identical pen injectors and cartons to maintain blinding of the study.

The IWRS will be programmed with blind-breaking instructions. In case of an emergency, the investigator has the sole responsibility for determining if unblinding of a participant's treatment assignment is warranted. Participant safety must always be the first consideration in making such a determination. If the investigator decides that unblinding is warranted, the investigator is encouraged to contact the sponsor prior to unblinding a participant's treatment assignment unless this could delay emergency treatment of the participant. If a participant's treatment assignment is

unblinded, the sponsor must be notified within 24 hours after breaking the blind. The date and reason that the blind was broken must be recorded in the source documentation and case report form, as applicable.

7.5 Preparation/Handling/Storage/Accountability

1. The investigator or designee must confirm appropriate temperature conditions have been maintained during transit for all study treatment received and any discrepancies are reported and resolved before use of the study treatment.
2. Only participants enrolled in the study may receive study treatment, and only authorized site staff may supply or administer study treatment. All study treatments must be stored in a secure, environmentally controlled, and monitored (manual or automated) area in accordance with the labelled storage conditions with access limited to the investigator and authorized site staff.
3. The investigator, institution, or the head of the medical institution (where applicable) is responsible for study treatment accountability, reconciliation, and record maintenance (ie, receipt, reconciliation, and final disposition records).
4. Further guidance and information for the final disposition of unused study treatment are provided in the Study Reference Manual.

7.6 Treatment Compliance

Study treatment compliance will be closely monitored by assessing the participant's daily reporting of self-administered study treatment on the electronic hand-held device. Before dispensing new study treatment, study site personnel will make every effort to collect all used and unused study treatment.

In the event of early termination, compliance will be assessed using the available daily reports on the hand-held device and/or by the coordinator depending on when the termination occurs. In the event of AE or intercurrent illness, dosing of study treatment can be stopped temporarily, for a maximum duration of 3 days. Should longer cessation of dosing be necessary, the investigator should contact the sponsor (Section 8.1.1).

The study centers will keep an accurate drug disposition record that specifies study treatment dispensed to each participant and the date of dispensing.

7.7 Concomitant Therapy

Any medication or vaccine (including over-the-counter or prescription medicines, vitamins, and/or herbal supplements) that the participant is receiving at the time of enrollment or receives during the study must be recorded on the electronic case report form (eCRF) along with:

- Reason for use
- Dates of administration including start and end dates
- Dosage information including dose and frequency

As much as possible, the dose and frequency of all concomitant medications taken for chronic conditions with the exception of diabetes mellitus (see Section 7.7.2—Permitted Treatments) should be held stable during the study. The sponsor should be contacted if there are any questions regarding concomitant or prior therapy.

7.7.1 Prohibited Treatments and Washout Before the Study

The classes of drugs prohibited in the study are, with the exception SLGT-1 and SGLT-2 inhibitors, those that affect GI motility, either positively or negatively, and therefore could confound the assessment of the efficacy of study treatment on the signs and symptoms of DG. The SGLT-1 and SGLT-2 inhibitors are prohibited. Their mechanism of action is through causing increased glycosuria, which may affect interpretation of the GEBT results.

Table 7–2 provides a list of drug classes and treatments that are prohibited during this study and require washout during the Run-in Periods of the current study and the lead-in Studies (RLM-MD-01 or RLM-MD-02).

Table 7–2 Prohibited Medications and Washout Requirements

Drug Class/Treatment	Washout Required Prior to Baseline
Sodium-glucose co-transporter-2 (SGLT-1 or SGLT-2) inhibitors: Empagliflozin, canagliflozin, dapagliflozin, etc.	Prohibited only 3 days prior to the GEBT done in a subset of participants at a subset of sites at Visit 4 or the Early Termination Visit
Pro-motility agents: Metoclopramide, macrolide antibiotics (eg, erythromycin, clarithromycin, azithromycin), domperidone, prucalopride, or other drugs considered to be GI pro-motility agents	Rollover Participants: 10 days prior to the start of the Run-in Period of the Lead-in study De novo Participants: 10 days prior to the start of the Run-in Period of this study, RLM MD-04
Anticholinergics: Drugs with an anti-cholinergic mechanism of action as the basis of their therapeutic benefit, not those that have anti-cholinergic activity as a side effect	
Anti-emetics (Used for more than 1 day a week, or participant requires an anti-emetic drug once weekly repeatedly (ie, for 3 consecutive weeks or more), the investigator should contact the sponsor to discuss the safety of the participant continuing study treatment.)	
Amylin analogue: pramlintide	
5HT4 agonists (cisapride, tegaserod, and prucalopride)	
Opioids^a (eg, tramadol)	Washout period is not applicable as the use of opioids is not allowed. See Exclusion Criteria #12 and #13.
Glucagon-like peptide-1 (GLP-1) agonists: Exenatide, liraglutide, etc.	Rollover Participants: 6 weeks prior to the start of the Run-in Period of the Lead-in study De novo Participants: 6 weeks prior to the start of the Run-in Period of this study, RLM MD-04
Botulinum toxin injections (eg, Botox®) by pyloric injection only; injection of Botox in other parts of the body is allowed	6 months prior to screening (Visit –2)

^a Exception to prohibition: An opioid prescribed for severe pain following a surgical operation, dental procedure, or injury may be taken as directed for up to 72 hours a maximum of two times during the study.

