Section 6.4 Screen Failures	Added option for the sponsor to permit a participant with a positive urine drug screen at Screening to continue in the Screening Period while confirmatory urine drug screen testing by a more specific method is carried on an aliquot of the original sample.	
Section 7.1 Treatments Administered	
Clarified that the first dose of study treatment is to be administered within approximately 30 minutes before the morning meal and the second daily dose is to be administered approximately 30 minutes before the evening meal.
 
Deleted option for investigator to contact sponsor if the participant could not inject study treatment into abdomen.
	
Section 7.4 Blinding/Masking	Unblinding procedures modified; requirement of investigator to notify sponsor prior to unblinding modified to encouraging the investigator to notify the sponsor prior to unblinding, but requiring notification within 24 hours after breaking the blind.	
Section 7.7.1 Prohibited Treatments and Washout Before the Study	SLGT-1 added to same rules for SGLT-2. Addition of details to the requirement of prohibiting SGLT-1 and SGLT-2 inhibitors.	

Section Number	Description of Change	Rationale
Section 7.7.1, Table 7-2 Prohibited Medications and Washout Requirements	
 • Amended information regarding SGLT-2 inhibitors as noted above and by adding SLGT-1 to same drug class/treatment as SGLT-2, rearranged rows by washout period, added tramadol as an example of opioid. • Pro-motility agents, anticholinergics, anti-emetics, amylene analogue, 5HT4 agonists, and glucagon-like peptide-1 – added washout requirements for de novo participants • Updated description of anti-emetics. • Added row for 5HT4 agonists. • Amended washout period for opioids from “10 days prior to the start of the Run-in Period” to Not applicable since use of opioids is not allowed and referenced exclusion criteria #12 and #13. 	
Section 7.7.3 Rescue Medicine	
 • Specified that the day prior to and day of clinic visits are “during the Treatment Period”. • Deleted antihistamines as an example of an anti-emetic drug. • Revised to require investigator to contact (ie, “should contact) sponsor if participant requires anti-emetic more than 1 day/week or once weekly repeatedly instead of making it optional for investigator to contact (ie, “should consider contacting). 	

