Approximately 5000 participants will be screened in lead-in Studies RLM-MD-01 and RLM-MD-02. Participants who do not meet certain randomization criteria may enter this study directly if they meet enrollment criteria defined below.

Study Population:

Two different groups of participants may enter the study:

- Participants who met all Screening and Run-in Period criteria in lead-in Study RLM-MD-01 or lead-in Study RLM-MD-02 (including compliance with dosing and data entry into the Diabetic Gastroparesis Symptom Severity Diary [DGSSD] during the lead-in study Run-in Period), but were not randomization-eligible at the end of the lead-in study Run-in Period, are eligible for randomization in Study RLM-MD-04 if:
 - They had no vomiting episodes recorded in the DGSSD and had an average daily DGSSS ≥ 12 at the end of the lead-in study Run-in Period.

OR

- They had vomiting episodes recorded in the DGSSD but had an average daily DGSSS of ≥ 12 and < 16 at the end of the lead-in study Run-in Period.

In the current study, these “**rollover participants**” will enter the study at Visit 1 (Randomization); they will not undergo Screening (Visit -2) or Run-in Visit (Visit -1) procedures.

2. Patients who undergo screening and run-in procedures in Study RLM-MD-04 are “**de novo participants**”. To be eligible for randomization in the current study, de novo participants must meet all Screening and Run-in Period criteria for Study RLM-MD-04, including:

At the Screening Visit (Visit -2):

- Male or female aged 18 years and older;
- T1DM or T2DM with controlled and stable blood glucose levels and HbA1c $\leq 11\%$;
- Symptoms suggestive of DG for at least 3 months (one of which must be nausea), with mechanical obstruction of the gastrointestinal (GI) tract as the cause of symptoms having been ruled out;
- History of nausea and/or at most a single episode of vomiting in the 2 weeks prior to Screening (Visit -2), as ascertained by participant history

[figure not shown]
At the End of the Run-in Period:

- Evidence of compliance during the Run-in Period with both the use of the electronic hand-held device for entry of data and with twice daily SC injections of the study treatment;
- No treatment with GI promotility agents during the Run-in Period;
- A score of ≥ 12 for the average of the daily DGSSS measured during the Run-in Period.

[figure not shown]
Number of Sites:

Approximately 700 sites globally (the combined number of sites from Studies RLM-MD-01 and RLM-MD-02).

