5.1 Overall Design

- Global, multicenter, randomized, double-blind, placebo-controlled, parallel-group
- Treatment Groups: Relamorelin 10 µg and placebo; BID, SC
- Study Duration: 52-week Treatment Period.

See [Figure 5-1](#) for a Study Schematic.

Figure 5-1 RLM-MD-04 Study Schematic

Study Population:

Two different groups of participants may enter into the study:

- Participants who met all Screening and Run-in Period criteria in lead-in Study RLM-MD-01 or lead-in Study RLM-MD-02 (including compliance with dosing and data entry into the DGSSD during the lead-in study Run-in Period), but were not randomization-eligible at the end of the lead-in study Run-in Period, are eligible for randomization in Study RLM-MD-04 if:

- They had no vomiting episodes recorded in the DGSSD and had an average daily DGSSS ≥ 12 at the end of the lead-in study Run-in Period.

OR

- They had vomiting episodes recorded in the DGSSD but had an average daily DGSSS of ≥ 12 and < 16 at the end of the lead-in study Run-in Period.

In the current study, these “**rollover participants**” will enter the study at Visit 1 (Randomization); they will not undergo Screening (Visit -2) or the Run-in Visit (Visit -1) procedures

2. Patients who undergo screening and run-in procedures in Study RLM-MD-04 are “**de novo participants**”. To be eligible for randomization in the current study, de novo participants must meet all Screening and Run-in Period criteria for Study RLM-MD-04, including:
 - a. At Screening, be male or female age 18 years and older; T1DM or T2DM with controlled and stable blood glucose levels and HbA1c \leq 11%; symptoms suggestive of DG for at least 3 months (one of which must be nausea), with mechanical obstruction of the GI tract as the cause of symptoms having been ruled out.
 - b. History of nausea and/or at most a single episode of vomiting in the 2 weeks prior to Screening (Visit -2), as ascertained by participant history
 - c. During the Run-in Period, delayed GE by gastric emptying breath test (GEBT)
 - d. After Run-in Period: Evidence of compliance during the Run-in Period with the use of the electronic hand-held device for entry of data, with twice daily SC injections of the study treatment, and no treatment with GI promotility agents; a score of \geq 12 for the average of the daily DGSSS measured during the Run-in Period.

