6.1.2 De Novo Participants

Participants who undergo screening and run-in procedures for Study RLM-MD-04 are eligible to be included in the study if all of the following criteria apply:

1. Male or female participants aged 18 years or older at Screening (Visit –2)
2. T1DM or T2DM of at least 5 years' duration, with controlled and stable blood glucose levels (ie, no episodes of diabetic ketoacidosis, Hyperosmolar Hyperglycemic Nonketotic Diabetic Syndrome, or severe hypoglycemia within the 6 months preceding Screening [Visit –2])
3. HbA1c \leq 11.0% at Screening (Visit –2) in participants being treated with oral and/or parenteral medications for T1DM or T2DM with the goal of achieving controlled and stable glucose levels
4. DG defined as at least a 3-month history prior to Screening (Visit –2) of symptoms (one of which must be nausea) on an ongoing basis that are suggestive of GP (eg, nausea, abdominal pain, postprandial fullness, bloating, vomiting, and early satiety)
5. Female participants willing to minimize the risk of inducing pregnancy for the duration of the clinical study and Follow-up Period
A female participant is eligible to participate if she is not pregnant (has a negative urine pregnancy result prior to randomization; see [Appendix 5](#)), not breastfeeding, and at least one of the following conditions applies:
 - a. Not a woman of childbearing potential (WOCBP) as defined in [Appendix 5](#)
OR
 - b. A WOCBP who agrees to follow the contraceptive guidance in [Appendix 5](#) during the Treatment Period and for at least 7 days after the last dose of study treatment
6. Documentation of absence of an obstructing lesion on upper GI series with contrast or upper endoscopy, performed at some time before the Run-in period (Visit 2) but after the appearance of symptoms that led to the diagnosis of DG
7. Nausea and/or at most a single episode of vomiting during the 2 weeks prior to Screening (Visit –2), as ascertained by participant history
8. Delayed GE confirmed by abnormal GEBT, defined as GE half-time ($t_{1/2}$) \geq 79 minutes at the start of the placebo-controlled Run-in Period (Visit 2 of RLM-MD-01, RLM-MD-02, or this study). In countries where the GEBT is not available, delayed GE may be confirmed by abnormal scintigraphy result ($>$ 60% retention at 2 hours or $>$ 10% at 4 hours). Refer to the Study Reference Manual
9. The BMI criterion has been removed.

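### Section 7.7.1 and Table 7-2 contradict each other on SGLT inhibitors, and the table row leaves out the entry breath test; exclusion criteria 11 and 14 state lengths of use where Table 7-2 sets drug-free intervals

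*Protocol*

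**What the plan says.** **SGLT inhibitors.** The body of protocol section 7.7.1 is unqualified: "The SGLT-1 and SGLT-2 inhibitors are prohibited". The reason given is increased glycosuria, "which may affect interpretation of the GEBT results". The sentence introducing Table 7-2 adds that the listed classes are not allowed in the study and need washout in the Run-in Periods of this study and the lead-in studies. The SGLT row of the table, in a column headed as washout before baseline, is narrower: "Prohibited only 3 days prior to the GEBT done in a subset of participants at a subset of sites at Visit 4" or at the Early Termination Visit.

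**Entry test.** Section 5.1 requires of de novo participants "During the Run-in Period, delayed GE by gastric emptying breath test (GEBT"). Inclusion criterion 8 (section 6.1.2) sets the threshold at a half-time of at least 79 minutes, times the test at the start of Run-in, and labels it "Visit 2 of RLM-MD-01, RLM-MD-02, or this study". It allows an alternative: "In countries where the GEBT is not available, delayed GE may be confirmed by abnormal scintigraphy result". It then refers the reader to the Study Reference Manual.

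**Exclusion criteria 11 and 14** (section 6.2.3). Criterion 11 excludes use of pro-motility drugs for at least 10 days before Run-in. Criterion 14 excludes GLP-1 agonist treatment for at least 6 weeks before Run-in. Table 7-2 gives the same 10 days and 6 weeks as washout periods.

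**The concern.** Delayed gastric emptying is the objective entry test, alongside patient-reported symptoms. The protocol says one drug class can affect how that test is read, yet the operative table row restricts the class only around a later GEBT done in a subset. The word *only* in the row shuts out the entry test. Section 7.7.2 expects most participants to be on glucose-lowering prescriptions and encourages adjusting them, so exposure at entry is plausible.

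Two sites could therefore act differently. One following the body text would bar the drug throughout. One following the row would allow it on the day of the entry GEBT. At stake is how securely GEBT-qualified de novo participants can be said to have delayed emptying.

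For criteria 11 and 14, a site checking only the exclusion list would apply a different rule from a site checking Table 7-2.

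**Working it through.** No formula or stated figure is involved. The check sets the texts side by side and tests each against a concrete case.

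**1. SGLT inhibitor taken on the day of the entry GEBT (de novo)**

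| Text | Result |
|---|---|
| 7.7.1 body, prohibition sentence | Not allowed |
| 7.7.1 body, Run-in washout sentence | Washout required in Run-in |
| Table 7-2, SGLT row | Allowed; the hold applies only before the Visit 4 or Early Termination GEBT |
| De novo exclusion list, 6.2.3 | No SGLT item |

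The first two lines cannot stand with the third. The washout sentence does not settle the matter either. The entry GEBT is done at the start of Run-in, so a washout that takes place during Run-in does not guarantee any drug-free days before the test. The reason in 7.7.1 refers to GEBT results in general and draws no line between the entry test and later ones.

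**2. Who is affected**

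Only de novo participants who qualify by GEBT. Those qualified by scintigraphy fall outside, because the stated reason concerns the breath test. Rollover participants also fall outside: "they will not undergo Screening (Visit -2) or Run-in Visit (Visit -1) procedures". Their emptying test was done under the lead-in protocols, which are not among the documents.

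**3. Visit label**

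In this study the Run-in visit is Visit -1 (Synopsis; exclusion criteria 11 and 14), Visit 1 is randomization and Visit 4 is Day 84 (section 9.1.1). A Visit 2 of this study would fall after randomization and cannot be the entry test. Criterion 8 needs Visit -1 for this study. Inclusion criterion 6 labels the Run-in period Visit 2 as well.

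**4. Criteria 11 and 14 read literally**

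- Metoclopramide for 5 days, ending the day before Run-in. Criterion 11: 5 < 10 days of use, so not excluded. Table 7-2: the 10-day drug-free interval is not met.
- A GLP-1 agonist for 3 weeks up to Run-in. Criterion 14: 3 × 7 = 21 days of use, below 6 × 7 = 42 days, so not excluded. Table 7-2: the 42-day drug-free interval is not met.

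Exclusion criterion 15 (pyloric botulinum toxin) is written as a look-back window of 6 months before screening. That suggests criteria 11 and 14 were meant the same way and are drafting errors.

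**The case against.** **A hold may exist elsewhere.** The Schedule of Activities is not reproduced in the available text, and criterion 8 itself points to the Study Reference Manual. Either could require a hold before the entry GEBT. This stands, so it cannot be said that sites had no such instruction. It would not remove the conflict inside section 7.7.1.

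**The drug is not unregulated.** A reader of the table row alone might infer that SGLT inhibitors had no rule at entry. The documents do not support that: the body text prohibits them and calls for Run-in washout. Section 7.7.2 also tells sites to ask the sponsor when permissibility is in doubt. The defect is a conflict between body text and table.

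**The narrow row may be deliberate.** Section 7.7.1 separates SGLT inhibitors from the classes that affect motility, so a different rule for them is not odd in itself. The amendment summary lists the classes for which it "added washout requirements for de novo participants" and treats the SGLT change separately, as an addition of detail. A change log is weak evidence either way. Deliberate or not, the row covers one GEBT and omits another to which the same reason applies.

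**Table 7-2 governs washout.** This stands for criteria 11 and 14. A reader might infer that short courses of pro-motility drugs or GLP-1 agonists were permitted up to Run-in. They were not, because the table applies in its own right.

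**Nothing in the report depends on it.** This also stands. The SAP is abbreviated, efficacy is descriptive only (SAP section 10.0), and the visible SAP text plans no summary of GEBT or delayed emptying.

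**Conclusion.** The point holds as a minor internal-consistency correction. Section 7.7.1 contradicts itself on SGLT inhibitors, and the Table 7-2 row as written allows one on the day of the entry GEBT. Criteria 11 and 14 conflict with Table 7-2 in wording, with no loss of the washout requirement.

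The size and direction of any misclassification of delayed emptying are unknown. The documents give no rate of SGLT inhibitor use, no de novo share, and no direction for the effect on half-time.

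A reader might go further and infer a biased treatment comparison. The documents do not support that: the entry test comes before randomization, so any misclassification bears on who enters and not on the contrast between arms.

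The conclusion assumes that the unseen Schedule of Activities and Study Reference Manual do not override the table row. The study was terminated on 04 September 2020 (SAP section 4.0), so the edits matter only if these criteria are reused.

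**What to change.** - **Table 7-2 SGLT row and the matching sentence in 7.7.1:** prohibited for 3 days before every GEBT, including the entry GEBT at the start of Run-in (Visit -1), Visit 4 and Early Termination.
- **Inclusion criterion 8:** for this study, replace Visit 2 with Visit -1, and correct the same label in criterion 6.
- **Exclusion criterion 11:** any use of the listed drugs within 10 days before Run-in begins (Visit -1).
- **Exclusion criterion 14:** any GLP-1 agonist use within 6 weeks before Run-in begins (Visit -1).

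The cost is a few wording edits and, for participants on these drugs, one more 3-day SGLT inhibitor hold, of the length the protocol already accepts before Visit 4. No change to the SAP or the abbreviated report is needed.
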